### 8.2 Exclusion Criteria

All subjects meeting any of the following criteria will be excluded from this study:

1. Female patients who are pregnant or lactating
2. Patients with any history of seizure or seizure at stroke onset
3. Presence or history of any other condition or finding that, in the investigator's opinion, makes the patient unsuitable as a candidate for the SENSE device monitoring or study participation or may confound the outcome of the study
4. Any intraventricular hemorrhage on the diagnostic (pre-enrollment) CT with planned placement of an intraventricular catheter
5. Secondary cause of ICH suspected (e.g., arteriovenous malformation, cavernoma, aneurysm, hemorrhagic transformation ischemic stroke, venous sinus thrombosis, trauma)
6. Planned withdrawal of care within 24 hours of enrollment
7. Planned surgical evacuation within 24 hours of enrollment
8. Current participation in a medical or surgical interventional clinical trial
9. Presence of subdural, epidural or aneurysmal subarachnoid hemorrhage on diagnostic scan

10. Planned continued use or prescribed use during the study of medications that, in the investigator's best clinical judgment, are known or suspected to lower the seizure threshold
11. Planned continued use of medications that, in the investigator's best clinical judgment, could increase the chances for subsequent uncontrolled hemorrhage
12. Planned or current use of continuous EEG monitoring

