### 10.2 Stopping Rules

Consistent with usual procedures for the conduct of first-in-man studies, a priori specific guidelines are described below for stopping the study when the threshold for an excess number of safety events is reached. Stopping rules are based on the methods proposed by Moye.

The occurrence of seizures is the main adverse event of interest for this study. Seizures are defined as clinical tonic-clonic activity that occurs during the 72 hours of SENSE monitoring. Using the binomial observed event rate, the associated lower 90% confidence interval will be calculated for the observed event. The stopping decision is based on when the assumed true event rate, set at 16%, falls below the lower 90% confidence interval for the observed rate which is dependent upon the number of subjects accrued.

Using these parameters, the study is stopped if there are:

- 3 subjects with occurrence of seizure after SENSE monitoring within the first 6 subjects
- 4 subjects with occurrence of seizure after SENSE monitoring within the first 10 subjects

---

 Fundamentals for investigators. Lemuel A. Moyé, Springer, New York, 2003. No. of pages: xxiii+436.

The table below shows the observed event rate and the lower 90% confidence interval for that rate for the number of subjects enrolled at the stage when the allowed number of observed subjects with seizure changes. The allowed number of subjects with seizure is based on the assumed event rate, 16%, falling below the 90% CI for the observed rate as stated above.

Table: Seizure Threshold Rates for an Assumed True Event Rate of 16%

Subjects Enrolled	Number of Seizures (S)	Observed Event Rate	Lower 90% CI for Observed Event Rate
6	3	0.50	0.16
7	3	0.43	0.12
7	4	0.57	0.26
9	4	0.44	0.17
10	4	0.40	0.14
10	5	0.50	0.24

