Lopez-Martin et al. studied the effects of 2 hours of Global System for Mobiles (GSM)-modulated 900 MHz radiation (simulating cellular phone-type radiation) in a picrotoxin induced rat seizure model. Rats pre-treated with subconvulsive doses of picrotoxin and exposed to radiation suffered seizures and had increased cerebral levels of neuronal activity marker c-Fos. However, rats exposed to radiation but not pretreated with picrotoxin did not suffer seizures and cerebral c-Fos levels were significantly lower. From this, the authors concluded cellular phone type radiation could induce seizures in rats with a picrotoxin induced lowering of the seizure threshold but not in rats exposed to GSM-type radiation alone. Carballo-Quintas et al. reported similar results in picrotoxin treated rats exposed to 90 minutes, 24, or 72 hours of 900 MHz electromagnetic field.

Curcio et al. evaluated brain electroencephalogram (EEG) activity in 12 patients with focal epilepsy under acute real and sham exposure for 45 minutes of GSM-like electromagnetic fields in a double-blind crossover design. EEGs were obtained before, during, and after the GSM-like exposure. Observed EEG spiking activity (spike count) tended to be lower under real exposure than sham exposure. Acute GSM exposure resulted in slight changes in EEG quantitative indices without reaching any clinical relevance. From this experiment, the authors concluded there was no evidence of an increased risk of incoming seizures for these patients as a result of using mobile phones.

Based on the evaluation of the published literature and the *in vivo* porcine studies conducted by researchers from Sense Diagnostics, an increase in the rate of occurrence of seizures resulting from exposure to the SENSE device in this clinical study is unlikely, and any increase in the rate of seizures above that which is expected in this patient population would be a clinically significant adverse event that could warrant stopping the clinical trial, especially since study candidates with a history of seizure activity are excluded from the trial. Thus, in the absence of any human clinical experience with the SENSE device, the selection of seizures as the adverse event of interest is justified for this study based solely on the published literature.

---

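### The 16% seizure rate behind the stopping rule is not shown to fit the patients who are eligible or the event that is counted

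*Combined protocol and SAP*

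**What the plan says.** Section 10.2 sets the reference in these words: "The stopping decision is based on when the assumed true event rate, set at 16" percent, falls below the lower limit for the observed rate. On that limit it says only that "the associated lower 90% confidence interval will be calculated for the observed event". The footnote to the 16% cites "Guidelines for the Management of Spontaneous Intracerebral Hemorrhage: A Guideline for Healthcare Professionals" and gives no derivation, time window, seizure type or adjustment.

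Two bullets state when the study stops: "3 subjects with occurrence of seizure after SENSE monitoring within the first 6 subjects" and "4 subjects with occurrence of seizure after SENSE monitoring within the first 10 subjects".

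The counted event is defined in the same section: "Seizures are defined as clinical tonic-clonic activity that occurs during the 72 hours of SENSE monitoring".

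Section 8.2 excludes "Patients with any history of seizure or seizure at stroke onset" (criterion 2) and planned use of drugs that the investigator judges to lower the seizure threshold (criterion 10).

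The closing paragraph of Section 10.2 says that a seizure rate above the one expected in this population would be clinically significant and could warrant stopping, "especially since study candidates with a history of seizure activity are excluded from the trial".

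Section 9.7 has the independent safety monitor compare seizure incidence with the Section 10.2 rules when judging early termination of the study. Section 10.0 says there will be no separate SAP, so a justification of the 16% would have to be in this document.

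**The concern.** Section 10.2 relies on the exclusions when it explains why a small excess of seizures would matter. It then sets the boundary with a rate from a source on spontaneous hemorrhage in general, and never states the rate expected in the patients it will enroll. Removing people with earlier or onset seizures and those on threshold-lowering drugs would be expected to reduce the background. Counting only tonic-clonic events over 72 hours points the same way, unless the 16% already refers to such events.

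If the true background is below 16%, a device that raised the rate to 16% would sit exactly at the reference, and the rule would read the result as ordinary. Safety is one of the two primary objectives in Section 5.0, and seizure is the only event with a stopping rule.

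**Working it through.** **Inputs from the documents.** Reference rate 16%, the lower 90% limit, the two bullets and the threshold table (Section 10.2); up to 10 subjects (Section 7.0).

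**Input not in the documents.** The background rate in eligible patients. I assume 5%, 8% and 10% in turn, for illustration only.

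**Step 1. Reproduce the table.** The printed limits follow from the Wald formula L = r − 1.645 × √(r(1 − r)/n), with r = x/n, which is the lower end of a two-sided 90% interval. For 3 of 6: 0.50 − 1.645 × √(0.25/6) = 0.164.

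| Seizures / subjects | Computed | Printed |
|---|---|---|
| 3/6 | 0.164 | 0.16 |
| 3/7 | 0.121 | 0.12 |
| 4/7 | 0.264 | 0.26 |
| 4/9 | 0.172 | 0.17 |
| 4/10 | 0.145 | 0.14 |
| 5/10 | 0.240 | 0.24 |

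Five rows agree on rounding; 4/10 looks truncated.

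**Step 2. Chance that the bullets stop the study.** Let p be the true rate, X6 the number of subjects with seizure among the first 6, and Y4 the number among the next 4. Then

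P(stop) = P(X6 ≥ 3) + P(X6 = 2)P(Y4 ≥ 2) + P(X6 = 1)P(Y4 ≥ 3) + P(X6 = 0)P(Y4 = 4).

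At p = 0.15: 0.0473 + 0.1762 × 0.1095 + 0.3993 × 0.0120 + 0.3772 × 0.0005 = 0.072.

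The same formula gives 0.3% at p = 5%, 2.2% at 10% and 8.6% at 16%.

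**Step 3. Change only the reference.** I keep the plan's formula and, as in its bullets, count only crossings at three or more events. The limits for three events are 0.164 (of 6), 0.121 (of 7), 0.093 (of 8), 0.075 (of 9) and 0.062 (of 10). A lower reference therefore changes how long three events remain a crossing after the sixth subject. At p = 0.15, with subscripts giving the number of subjects:

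- 5% reference: P(X10 ≥ 3) = 1 − (0.1969 + 0.3474 + 0.2759) = 0.180.
- 8% reference: P(X8 ≥ 3) + P(X8 = 2)P(Y2 = 2) = 0.1052 + 0.2376 × 0.0225 = 0.111.
- 10% reference: P(X7 ≥ 3) + P(X7 = 2)P(Y3 ≥ 2) + P(X7 = 1)P(Y3 = 3) = 0.0738 + 0.2097 × 0.0608 + 0.3960 × 0.0034 = 0.088.

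| Reference | Stops at true 15% | Stops at true 5% |
|---|---|---|
| Bullets as written | 7.2% | 0.3% |
| 5% (assumed) | 18.0% | 1.2% |
| 8% (assumed) | 11.1% | 0.6% |
| 10% (assumed) | 8.8% | 0.4% |

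These rows show how sensitive the rule is to its reference. They are not proposed boundaries.

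**Step 4. How much is due to the reference?** The limit is 0.017 for 2 of 6 and 0.164 for 3 of 6, so the first bullet's count is the same for any reference from about 1.7% to 16.4%. The limit is 0.062 for 3 of 10 and 0.145 for 4 of 10, so the second bullet's count falls only if the reference is below about 6.2%. Even with a 5% reference, a doubling to 10% stops the study 7.0% of the time, against 2.2% as written.

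**The case against.** The strongest reply is that nobody can tell from these documents what the 16% counts. If the source already reports early clinical seizures, the arguments from window and event type fall away. This stands: only the direction of the gap is supported, and a reader should not infer that each selection can only lower the rate. The exclusion of continuous EEG (criterion 12) adds little, because clinical tonic-clonic activity needs no EEG to be seen.

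The second reply is that sample size dominates. This also stands. Sections 10.0, 10.1 and 10.8 describe a small feasibility study without statistical sizing or success criteria, and with a 10% reference almost nothing changes (8.8% against 7.2%).

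The third reply is that the count is not the only safeguard. The independent safety monitor reviews seizures in every subject for relation to the device (Section 9.7), and any possible seizure-related event is evaluated (Section 11.3). This is partial mitigation, since Section 9.7 ties study termination to the Section 10.2 rules.

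A reader might also take the closing paragraph of Section 10.2 as an admission that 16% is too high. It is not: the paragraph explains why seizure was chosen as the event of interest. It does set a standard relative to this population, which the reference is not shown to meet.

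Finally, a reader might obtain a larger contrast, about 7% against 22% at a true 15%, by letting the 5% reference stop at two events. That is not like for like. The bullets contain no two-event stop, although the plan's formula gives one at 16% as well (2 of 3 has a limit of 0.219).

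**Conclusion.** The point holds as an unjustified reference rate with a plausible direction of error. Section 10.2 applies 16% to a group selected against seizures and to a narrow event, without showing that it fits either, and its own standard refers to the rate expected in this population.

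The illustrated effect at a true 15% runs from slight (7.2% to 8.8%, 10% reference) to about 2.5-fold (7.2% to 18.0%, 5% reference). These figures rest on assumed background rates, the Wald limit, crossings at three or more events, and a check after every subject.

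The documents do not support the stronger inference that the exclusions disarm the rule, or that it is known to tolerate a device-related excess. No background rate is given, ten subjects limit any such rule, and with an assumed 5% reference a tripling to 15% would still go unstopped about 82% of the time (1 − 0.180). The point should be addressed because the rule governs a safety decision and the correction is cheap.

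**What to change.** Reconcile Section 10.2 with Section 8.2 and with its own closing paragraph. Base the reference on what the sponsor's source supports for subjects without prior or onset seizure, for tonic-clonic events and the 72-hour window. If the source gives no such rate, say so, label the reference an assumption, and show the rule's stopping probabilities over a range. Then regenerate the table and bullets from that rate by the plan's own method. The threshold remains for the sponsor and the independent safety monitor to set; none is proposed here.

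Two contradictions should be reconciled in the same revision. The second bullet stops at 4 of 10, although the table's limit there (0.14) is not above 16%. The bullets also speak of seizures after monitoring, whereas the definition says during it.

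The cost is one recalculated table, two bullets and a short justification. The downside is a slightly higher chance of stopping without a device effect: 1.2% rather than 0.3% if the true rate and the reference are both 5%.

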## 8.0 Subject Population

This is a single site study that will be conducted at the University of Cincinnati Medical Center (Cincinnati, OH). Up to 10 subjects will be enrolled and receive a headset for monitoring.

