### **9.7 Safety Monitoring**

The presence or absence of device related adverse events or complications, including epileptic seizures, occurring during the 72-hour SENSE monitoring period or emerging after the SENSE headset was removed (up to 7 days of hospital stay) will be documented.

A neurologist at the University of Cincinnati, who is not affiliated with the study or Sense Diagnostics, will serve as the independent safety monitor for this first-in-man study. The independent safety monitor will review adverse events and seizures for all subjects enrolled to detect any device related adverse events that may occur while the SENSE device is being worn or that emerged after exposure to the SENSE device. All adverse events, including seizures, determined to be device related will be recorded on the CRFs. The independent safety monitor will evaluate the incidence of seizures compared to the study stopping rules in Section 10.2 below to determine if early study termination is warranted.

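### Section 10.2 contradicts itself at ten subjects: the second bullet stops the study at 4 of 10 with seizure, but the plan's own table shows that the 16% criterion is not met there.

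*Combined protocol and SAP*

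**What the plan says.** Section 10.2 (Stopping Rules) sets one criterion, based on the binomial seizure rate observed so far. The study stops when the assumed true rate of 16% "falls below the lower 90% confidence interval for the observed rate which is dependent upon the number of subjects accrued".

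Two bullets follow, introduced by "Using these parameters, the study is stopped if there are". The first is 3 subjects with seizure within the first 6. The second is "4 subjects with occurrence of seizure after SENSE monitoring within the first 10 subjects".

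A table then lists observed rates and lower limits. The text says it shows "the number of subjects enrolled at the stage when the allowed number of observed subjects with seizure changes", and ties it to the same comparison: "The allowed number of subjects with seizure is based on the assumed event rate, 16%, falling below the 90% CI for the observed rate". Its rows are:

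| Subjects | With seizure | Observed rate | Lower 90% limit (printed) |
|---|---|---|---|
| 6 | 3 | 0.50 | 0.16 |
| 7 | 3 | 0.43 | 0.12 |
| 7 | 4 | 0.57 | 0.26 |
| 9 | 4 | 0.44 | 0.17 |
| 10 | 4 | 0.40 | 0.14 |
| 10 | 5 | 0.50 | 0.24 |

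Section 9.7 (Safety Monitoring) hands this section to the monitor: "The independent safety monitor will evaluate the incidence of seizures compared to the study stopping rules in Section 10.2 below". Section 8.0 caps the study: "Up to 10 subjects will be enrolled and receive a headset for monitoring".

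**The concern.** The bullets and the table are both presented as products of one criterion, so they should give the same decision at every sample size. At ten subjects they do not. The printed limit for 4/10 is 0.14, which leaves 16% above the limit, yet the second bullet stops the study there.

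The table's layout points the same way. At n=7 it pairs a row that fails (3/7) with one that passes (4/7), marking the move of the threshold from 3 to 4, and the bullets follow that move. At n=10 it pairs 4/10 (fails) with 5/10 (passes), marking a move from 4 to 5, and the second bullet does not follow it.

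This is the plan's only numerical stopping rule, and section 10.0 says that no separate SAP will be written. A monitor who sees 4/10 is told to stop by the bullet and not to stop by the criterion and its table. At stake are any device monitoring still running at that moment and whether the study is recorded as stopped by its safety rule.

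**Working it through.** **Inputs.** Reference rate 0.16, 90% confidence level, the two bullets and the six table rows, all from section 10.2; maximum of 10 subjects from section 8.0. The plan does not name the interval type or tail.

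**Step 1: reproduce the plan's column.** Take the normal-approximation (Wald) lower limit, L = p − z·√(p(1−p)/n), for a two-sided 90% interval (5% in the lower tail). For 4/10 the standard error is √(0.4 × 0.6/10) = 0.1549.

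| x/n | Printed | z = 1.65 | z = 1.645 | 0.16 < L? |
|---|---|---|---|---|
| 3/6 | 0.16 | 0.1632 | 0.1642 | yes, before rounding |
| 3/7 | 0.12 | 0.1199 | 0.1209 | no |
| 4/7 | 0.26 | 0.2628 | 0.2638 | yes |
| 4/9 | 0.17 | 0.1711 | 0.1720 | yes |
| 4/10 | 0.14 | 0.1444 | 0.1452 | **no** |
| 5/10 | 0.24 | 0.2391 | 0.2399 | yes |

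With z = 1.65 all six rows round to the printed values. With z = 1.645 five do, and 4/10 would print as 0.15. Either way 4/10 is under 0.16.

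**Step 2: could another interval rescue the bullet?**
- The exact (Clopper-Pearson) limit with a 5% tail gives 0.150 for 4/10, still under 0.16.
- A one-sided 90% Wald limit (z = 1.2816) gives 0.2015 for 4/10, which would pass. It also gives 0.189 for 3/7, where the table prints 0.12.
- The 90% Wilson limit gives 0.194 for 4/10 and 0.186 for 3/7, with the same result.

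The last two would support the bullet only by contradicting the table.

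**Step 3: the boundary.** Under the table's method, the smallest count that meets the criterion is 3 at n=4 to 6, 4 at n=7 to 9, and 5 at n=10. At n=8, which is not printed, 3/8 gives 0.093 and 4/8 gives 0.209. The bullets amount to 3 up to n=6 and 4 at n=7 to 10, so from n=4 to n=9 they agree and at n=10 they differ.

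At n=1 to 3 the formula also passes 1/1 and 2/2 (the standard error is zero, so the limit is 1.0) and 2/3 (0.219), although no bullet stops there. The comparison in step 4 leaves these out and uses 3 for every n up to 6 in both versions.

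**Step 4: size.** Assume independent subjects, a constant true rate and a look after each subject. The table boundary is 3 to n=6, 4 to n=9 and 5 at n=10. An exact recursion over the ten subjects gives:

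| True rate | Ever stop, bullets | Ever stop, table boundary | First stop at n=10, bullets |
|---|---|---|---|
| 16% (plan) | 8.6% | 7.1% | 1.5% |
| 24% (illustrative) | 24.2% | 20.1% | 4.1% |
| 32% (illustrative) | 44.8% | 38.2% | 6.6% |

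The chance of stopping by n=9 is the same in both versions (7.1%, 20.1%, 38.2%), so the whole difference arises at the tenth subject. Under the table boundary a first stop at n=10 is impossible: a study still open after nine subjects has at most 3 with seizure, hence at most 4 of 10, and 5 are needed.

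**The case against.** The strongest reply is that this hardly matters. The versions differ only if the fourth subject with seizure is first counted at the tenth subject. No further enrolment could be prevented by then. The bullet is the more cautious version, and at a true rate of 16% the stopping probabilities differ by only 1.5 percentage points. The only sentence saying when the study is stopped introduces the bullets, section 10.2 calls its rules guidelines, and its closing discussion says any rise in seizures above expectation could warrant stopping. A monitor facing 40% against 16% therefore has grounds to stop in any case.

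These points limit the consequence and argue for a modest grade. They do not remove the contradiction. The bullets are expressly derived from the criterion, and the closing discussion sets no number that would settle 4/10.

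A second objection is that the table boundary in step 4 is partly reconstructed, because the table has no rows below n=6 or at n=8. That is fair. The criterion applied literally from the first subject, under the Wald limit with z = 1.645, would stop with probability 20.9%, 35.9% and 52.7% at the three rates, because of what happens at n=1 to 3. The figures in step 4 isolate the disagreement at n=10 and do not describe that literal rule. The 4/10 conflict needs no reconstruction, since it is visible from the printed 0.14.

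**Conclusion.** The point holds. The second bullet disagrees with the criterion it is said to follow from and with the plan's own table: at 4/10 the printed limit is 0.14 against a reference of 0.16. The table value is sound under a standard method, so neither a misprint nor rounding explains the mismatch.

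The disagreement is confined to n=10 within the range n=4 to 10. It is worth 1.5 percentage points of stopping probability at a true rate of 16%, and 4.1 and 6.6 points at the illustrative rates of 24% and 32%, given a look after each subject and the boundary in step 3. It should be fixed because the safety monitor is told to use this section and nothing else in the plan resolves it. Which threshold should stand is not decided here.

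**What to change.** Reconcile the criterion, the two bullets and the table so that they give one decision at every n where the rule applies. The sponsor and the independent safety monitor choose the threshold at n=10. In the same edit:

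- Name the interval and tail used for the table, or the replacement chosen.
- State that the bullets are the operative rule, or give the smallest n at which the criterion applies, so that 1/1, 2/2 and 2/3 are settled.
- Print the limits to three decimals, because 3/6 clears 0.16 only before rounding.
- If another interval is adopted, regenerate both bullets and the table from it. The change may reach beyond 4/10: the exact limit with a 5% tail would put 3/6 at 0.153, below 0.16, and would still pass 2/2 at 0.224.

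The cost is wording and one small table in section 10.2. No extra subjects or data are needed.
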